6.4.1. Nonresponder Imputation

A nonresponder imputation (NRI) method imputes missing values as non-responses and can be justified based on the composite strategy for handling intercurrent events (ICH E9 R1). This imputation procedure assumes the effects of treatments disappear after the occurrence of an intercurrent event defined by the associated censoring rule.

All categorical endpoints will utilize the NRI method after applying the primary censoring rule to patients who permanently discontinued study drug or were rescued (described in Section 6.4). Additionally, all primary and key secondary categorical endpoints will utilize NRI after applying the secondary censoring rule as sensitivity analyses. For analyses which utilize either of the censoring methods, randomized patients without at least 1 post-baseline observation will be defined as nonresponders for all visits.

6.4.2. Mixed Model for Repeated Measures

Mixed Model for Repeated Measures analyses will be performed on continuous endpoints to mitigate the impact of missing data. This approach assumes missing observations are missing-at-random (missingness is related to observed data) and borrows information from patients in the same treatment arm taking into account both the missingness of data through the correlation of the repeated measurements.

Essentially MMRM estimates the treatment effects had all patients remained on their initial treatment throughout the study. For this reason, the MMRM imputation implies a different estimand (hypothetical strategy [ICH E9 R1]) than the one used for NRI on categorical outcomes.

All continuous endpoints will utilize MMRM after applying the primary censoring rule. As sensitivity analyses, all secondary continuous endpoints will also utilize MMRM after applying the secondary censoring rule (Table JAHL.6.1).

6.4.3. Modified Last Observation Carried Forward

For continuous measure, a modified last observation carried forward (mLOCF) imputation technique replaces missing data with the most recent non-missing post-baseline assessment. The specific modification to the LOCF is data after an intercurrent event will not be carried forward thus the mLOCF is applied after the specified censoring rule is implemented. The mLOCF assumes the effect of treatment remain the same after the event that caused missing data as it was just prior to the missing data event. Analyses using mLOCF require a nonmissing baseline and at least 1 postbaseline measure otherwise the data is missing for analyses purposes. Analyses using mLOCF help ensure the number of randomized patients who were assessed post-baseline

is maximized and is reasonable for this data as data directly prior to an intercurrent event (such as initiation of rescue therapy or drop out) is likely a non-efficacious response.

All continuous efficacy and health outcomes endpoints will use with mLOCF imputation methodology with an ANCOVA as sensitivity analyses to the MMRM analyses.

6.4.4. Placebo Multiple Imputation

The Placebo Multiple Imputation (pMI) methodology will be used as a sensitivity analysis for the analysis of the primary efficacy endpoint (IGA 0 or 1 at Week 16) as well as the key secondary endpoints at Week 16. In these sensitivity analyses the primary censoring rule will be applied.

The pMI assumes that the statistical behavior of drug- and placebo- treated patients after the occurrence of intercurrent events will be the same as if patients were treated with placebo. Thus, in the effectiveness context, pMI assumes no pharmacological benefit of the drug after the occurrence of intercurrent events but is a more conservative approach than mLOCF because it accounts for uncertainty of imputation, and therefore does not underestimate standard errors, and it limits bias. In the efficacy context pMI is a specific form of a missing not at random analysis and expected to yield a conservative estimate of efficacy.

In the pMI analysis, multiple imputations are used to replace missing outcomes for drug- and placebo-treated patients who have an intercurrent event using multiple draws from the posterior predictive distribution estimated from the placebo arm. The binary outcomes will then be derived from the imputed data.

Data are processed sequentially by repeatedly calling SAS® PROC MI to impute missing outcomes at visits $t=1, \dots, T$.

1. *Initialization:* Set $t=0$ (baseline visit)
2. *Iteration:* Set $t=t+1$. Create a data set combining records from drug- and placebo-treated patients with columns for covariates \mathbf{X} and outcomes at visits $1, \dots, t$ with outcomes for all drug-treated patients set to missing at visit t and set to observed or imputed values at visits $1, \dots, t-1$.
3. *Imputation:* Run Bayesian regression in SAS® PROC MI on this data to impute missing values for visit t using previous outcomes for visits 1 to $t-1$ and baseline covariates. Note that only placebo data will be used to estimate the imputation model since no outcome is available for drug-treated patients at visit t .
4. Replace imputed data for all drug-treated patients at visit t with their observed values, whenever available up to permanent study drug discontinuation and/or rescue (if censoring on rescue). If $t < T$ then go to Step 2, otherwise proceed to Step 5.
5. Repeat steps 1-4, m times with different seed values to create m imputed complete data sets.

Analysis: For continuous endpoints, fit its treatment response model (MMRM) for each completed data set. For the primary and secondary key efficacy endpoints [IGA (0,1), EASI75,

EASI90, SCORAD75, and 4-point improvement from baseline in Itch NRS], the binary outcomes will be derived from the imputed data for each patient before fitting the logistic regression model.

The number of imputed data sets will be $m=100$ and a 6-digit seed value will be pre-specified for each analysis. Within the program, the seed will be used to generate the m seeds needed for imputation. The initial seed values are given in [Table JAHL.6.2](#).

Table JAHL.6.2. Seed Values for Multiple Imputation

Analysis	Seed value
Proportion of patients achieving IGA of 0 or 1 with a ≥ 2 -point improvement from baseline at Week 16 using the primary censoring rule	123450
Percent change from baseline in EASI score at 16 weeks using the primary censoring rule. EASI75 and EASI90 will leverage imputation from EASI and therefore do not need a new seed number.	123451
Proportion of patients achieving SCORAD75 at 16 week using the primary censoring rule, with data up to rescue	123452
Proportions of patients achieving a 4-point improvement from baseline in Itch NRS at Week 16 using the primary censoring rule	123453
Mean change from baseline in Skin Pain NRS at Week 16 using the primary censoring rule	123454
Mean change from baseline in the score of Item 2 of the ADSS at Week 16 using the primary censoring rule	123455

Abbreviations: ADSS = Atopic Dermatitis Sleep Scale; EASI = Eczema Area and Severity Index score; IGA = Investigator's Global Assessment for AD; NRS = Numeric Rating Scale; SCORAD = SCORing Atopic Dermatitis.

The final inference on treatment difference is conducted from the multiple datasets using Rubin's combining rules, as implemented in SAS® PROC MIANALYZE.

6.4.5. Tipping Point Analyses

To investigate the missing data mechanism, sensitivity analyses using multiple imputation (MI) under the missing not at random assumption will be provided for the following primary and key secondary objectives:

- IGA (0,1) with ≥ 2 -point improvement at Week 16, baricitinib 1-mg, 2-mg and 4-mg compared to placebo
- EASI percent change from baseline to Week 16, baricitinib 1-mg, 2-mg and 4-mg compared to placebo
- Itch NRS 4-point improvement from baseline to Week 16, baricitinib 1-mg, 2-mg and 4-mg compared to placebo

All patients in the ITT population will be included. Data after the occurrence of intercurrent events (after application of the primary censoring rule) will be set to missing.

Within each analysis, a most extreme case will be considered, in which all missing data for patients randomized to baricitinib 1-mg, 2-mg or 4-mg will be imputed using the worst possible

result and all missing data for patients randomized to placebo will be imputed with the best possible result. Treatment differences will be analyzed using logistic regression or ANCOVA (Section 6.1) as appropriate.

For continuous variables, the following process will be used to determine the tipping point:

1. To handle intermittent missing visit data, a Markov chain Monte Carlo method (SAS® Proc MI with MCMC option) will be used to create a monotone missing pattern.
2. A set of Bayesian regressions (using SAS® Proc MI with MONOTONE option) will be used for the imputation of monotone dropouts. Starting from the first visit with at least 1 missing value, the regression models will be fit sequentially with treatment as a fixed effect and values from the previous visits as covariates.
3. A delta score is added to all imputed scores at the primary time point for patients in the baricitinib treatment groups, thus worsening the imputed value. The delta score is capped for patients based on the range of the outcome measure being analyzed.
4. Treatment differences between baricitinib and placebo are analyzed for each imputed dataset using ANCOVA (Section 6.1). Results across the imputed datasets are aggregated using SAS® Proc MIANALYZE in order to compute a p-value for the treatment comparisons for the given delta value.
5. Steps 3 and 4 are repeated, and the delta value added to the imputed baricitinib scores is gradually increased. The tipping point is identified as the delta value which leads to a loss of statistical significance (aggregated p-value >0.05) when evaluating baricitinib relative to the placebo group.

As a reference, for each delta value used in Steps 3 through 5, a fixed selection of delta values (ranging from slightly negative to slightly positive) will be added to imputed values in the placebo group, and Step 4 will be performed for the combination. This will result in a 2-d table, with the columns representing the delta values added to the imputed placebo responses, and the rows representing the delta values added to the imputed baricitinib responses. Separate 2-d tables will compare each baricitinib dose group to placebo.

A similar process will be used for the categorical variables:

1. Missing responses in the baricitinib groups will be imputed with a range of low response probabilities, including probabilities of 0, 0.1, and 0.2.
2. For missing responses in the placebo group, a range of responses probabilities (for example, probability = 0, 0.2 ... 1) will be used to impute the missing values. Multiple imputed datasets will be generated for each response probability.
3. Treatment differences between baricitinib and placebo are analyzed for each imputed dataset using logistic regression (Section 6.1). Results across the imputed datasets are aggregated using SAS® Proc MIANALYZE in order to compute a p-value for the treatment comparisons for the given response probability. If the probability values do not

allow for any variation between the multiple imputed datasets (for example, all missing responses in the placebo and baricitinib groups are imputed as responders and nonresponders, respectively), then the p-value from the single imputed dataset will be used.

The tipping point is identified as the response probability value within the placebo group that leads to a loss of statistical significance when evaluating baricitinib relative to placebo.

For tipping point analyses the number of imputed data sets will be $m=100$ and the seed values to start the pseudorandom number generator of SAS Proc MI (same values for MCMC option and for MONOTONE option) are given in [Table JAHL.6.3](#).

Table JAHL.6.3. Seed Values for Imputation

Analysis	Seed value
Proportion of patients achieving IGA (0,1) with ≥ 2 -point improvement at Week 16; primary censoring rule	123470
Proportion of patients achieving EASI75 at Week 16; primary censoring rule	123471
Proportion of patients achieving EASI90 at Week 16; primary censoring rule	
Proportions of patients achieving a 4-point improvement from baseline in Itch NRS at Week 16, primary censoring rule	123472
Proportion of patients achieving SCORAD75 at Week 16; primary censoring rule	123473

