- **H_{1,8,0}:** Mean change from baseline in Skin Pain NRS for baricitinib 1-mg patients is greater than or equal to the mean change from baseline in Skin Pain NRS for placebo patients at Week 16 [PAIN W16]
- **H_{1,9,0}:** Mean change from baseline in the score of Item 2 of the ADSS for baricitinib 1-mg patients is greater than or equal to the mean change from baseline in the score of Item 2 of the ADSS for placebo patients at Week 16 [ADSS2 W16]
- **H_{1,10,0}:** Proportion of baricitinib 1-mg patients achieving a 4-point improvement in Itch NRS is less than or equal to the proportion of placebo patients achieving a 4-point improvement in Itch NRS at Week 2 [ITCH W2]
- **H_{1,11,0}:** Mean change from baseline in the score of Item 2 of the ADSS for baricitinib 1-mg patients is greater than or equal to the mean change from baseline in the score of Item 2 of the ADSS for placebo patients at Week 1 [ADSS2 W1]
- **H_{1,12,0}:** Proportion of baricitinib 1-mg patients achieving a 4-point improvement in Itch NRS is less than or equal to the proportion of placebo patients achieving a 4-point improvement in Itch NRS at Week 1 [ITCH W1]

The multiple testing procedure is specified by [Figure JAHL.6.1](#).

[figure not shown]

Figure JAHL.6.1. Illustration of graphical multiple testing procedure with initial α allocation and weights.

The primary null hypotheses includes testing whether neither of baricitinib 4-mg and baricitinib 2-mg dose is superior to placebo at the primary endpoint defined as the proportion of placebo patients achieving IGA of 0 or 1 and ≥ 2 point improvement from baseline at Week 16. The initial alpha allocation is split evenly across these hypothesis to give them “equal footing”, i.e., $H_{4,1,0}$ and $H_{2,1,0}$ will each be first tested at a 2-sided alpha level of 0.025. Together with these primary hypotheses, multiplicity adjusted analyses will be performed on key secondary null hypotheses to control the overall family wise Type I error rate at a 2-sided alpha level of 0.05.

The graphical multiple testing procedure described in Bretz et al. (2011), which is a closed testing procedure will be used; hence it strongly controls the family-wise error rate across all endpoints (Alosh et al. 2014).

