If $H_{4,1,0}$ and $H_{2,1,0}$ are not rejected, no further testing is conducted as the α_0 for that test is considered “spent” and cannot be passed to other endpoints. If $H_{4,1,0}$ or $H_{2,1,0}$ is rejected, the testing procedure continues in either branches (starting with $H_{4,2,0}$ and $H_{2,2,0}$ respectively), with α propagated according to the directed edges and propagation weights displayed in [Figure JAHL.6.1](#). Each time a hypothesis is rejected, the graph is updated to reflect the reallocation of α , which is considered “recycled” by Alosh et al. (2014). This iterative process of updating the graph and reallocating α is repeated until all hypotheses have been tested or when no remaining hypotheses can be rejected at their corresponding α levels.

For Japan, the same testing strategy described in the [Figure JAHL.6.1](#) will be used, however, the proportion of patients achieving EASI75 and IGA of 0 or 1 at Week 16 are considered co-primary. Both endpoints have to meet statistical significance compared with placebo with a specific α level based on the graphical multiple testing procedure in order to demonstrate a superiority of a given baricitinib dose (baricitinib 4-mg and/or baricitinib 2-mg) compared with placebo. That is, $H_{4,1,0}$ and $H_{4,2,0}$ have to be rejected in order to demonstrate the superiority of baricitinib 4-mg compared with placebo and $H_{2,1,0}$ and $H_{2,2,0}$ have to be rejected in order to demonstrate the superiority of baricitinib 2-mg compared with placebo.

There will be no adjustment for multiple comparisons for any other analyses.

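### SAP 6.4.5 counts EASI percent change as tipped only above p = 0.05, although the claim is won at a Section 6.6 graph level that may be 0.025 or lower

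*SAP*

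**What the plan says.** SAP 6.4.5 announces "sensitivity analyses using multiple imputation (MI) under the missing not at random assumption will be provided for the following primary and key secondary objectives". It lists three Week 16 endpoints, each for 1-mg, 2-mg and 4-mg against placebo: IGA response, EASI percent change and 4-point Itch NRS improvement.

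For continuous variables, imputed baricitinib values are worsened by a growing delta and re-analysed by ANCOVA. The stopping rule carries a number: "The tipping point is identified as the delta value which leads to a loss of statistical significance (aggregated p-value >0.05"). EASI percent change is the only continuous endpoint on the list.

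The categorical part opens with "A similar process will be used for the categorical variables". For placebo, "a range of responses probabilities (for example, probability = 0, 0.2 ... 1) will be used to impute the missing values", and the tipping point is the placebo probability "that leads to a loss of statistical significance when evaluating baricitinib relative to placebo". No level is given.

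In SAP 6.6, EASI percent change is H4,4,0, H2,4,0 and H1,4,0 in the graphical procedure. The 4-mg and 2-mg IGA hypotheses "will each be first tested at a 2-sided alpha level of 0.025". After that, "Each time a hypothesis is rejected, the graph is updated to reflect the reallocation of" alpha. Alpha on a primary that is not rejected counts as used and is not passed on.

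Three other places bear on this. SAP 6.2 sets a 0.05 default and names the Section 6.6 strategy as an example of an exception. SAP 6.6 ends by leaving all other analyses unadjusted. SAP 6.11.3 gives the purpose of the sensitivity analyses as showing robustness.

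**The concern.** A tipping point answers one question: how bad must the missing data be before the result is lost? The answer is only meaningful if lost is measured against the bar by which the result was won. For EASI percent change that bar is the level the graph has placed on the hypothesis. Section 6.4.5 uses a fixed 0.05 for all three doses.

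Where the graph level is lower, some delta values give an aggregated p-value above the graph level but below 0.05. They are reported as not tipped although the claim would no longer stand. The reported delta is then too large, and most so for borderline results, where a tipping analysis matters most. What is at stake is the accuracy of a robustness statement, not the confirmatory decision.

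**Working it through.** **1. The plan's own figures.** The initial levels add up: 0.025 + 0.025 = 0.05, the family-wise level in SAP 6.6. The arms are 240 placebo and 120 per dose (SAP 5.1). The response rates are 10%, 25% (2-mg) and 30% (4-mg) (SAP 6.1). Power is Φ[(d − z·SE0)/SE1], with SE0 from the pooled rate and z = 2.2414 for two-sided 0.025.

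- 2-mg: pooled rate (24 + 30)/360 = 0.150. SE0 = √(0.1275 × 0.0125) = 0.0399. SE1 = √(0.09/240 + 0.1875/120) = 0.0440. Power = Φ[(0.15 − 2.2414 × 0.0399)/0.0440] = 91.5%.
- 4-mg: pooled rate (24 + 36)/360 = 0.167. SE0 = 0.0417, SE1 = 0.0461. Power = Φ[(0.20 − 2.2414 × 0.0417)/0.0461] = 99.0%.

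The stated power above 90% is reproduced, even at 0.025.

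**2. Bounds on the graph level.** The levels in the graph never total more than 0.05, so no hypothesis can have more than 0.05. Alpha leaves a hypothesis only when it is rejected. If one IGA primary is not rejected, it keeps its 0.025, and every rejected hypothesis has at most 0.05 − 0.025 = 0.025. This follows from the text of 6.6 whatever weights the figure contains. If both primaries are rejected, the level on EASI percent change depends on those weights and may be anything up to 0.05.

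**3. Size for the continuous endpoint where the level is 0.025.** The critical values are 1.9600 at 0.05 and 2.2414 at 0.025. At a fixed standard error the tipping delta is proportional to z minus the critical value, so the inflation is (z − 1.9600)/(z − 2.2414):

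| Assumed z | Calculation | Inflation |
|---|---|---|
| 3 | 1.0400 / 0.7586 | 1.37 |
| 4 | 2.0400 / 1.7586 | 1.16 |
| 5 | 3.0400 / 2.7586 | 1.10 |

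In SD units the excess is (2.2414 − 1.9600) × √(1/240 + 1/120) / m = 0.2814 × 0.1118 / m = 0.0315/m, where m is the fraction of baricitinib Week 16 values imputed. For assumed m of 10%, 20%, 30% and 50% this is 0.31, 0.16, 0.10 and 0.06 SD.

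**4. How often one primary fails.** I enumerated the binomial outcomes with a shared placebo arm and the SAP 6.1 rates. The range covers the second primary being tested at 0.05 (full recycling) or at 0.025 (none). With a pooled z-test, exactly one primary is rejected in 4.7% to 7.9% of trials and both in 92% to 95%. With a log odds ratio (0.5 added per cell), the range for exactly one is 4.7% to 8.2%. If the true 2-mg rate were 20%, which neither document states, it would be 26% to 36%.

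**5. Categorical endpoints, if 0.05 is meant.** Assumed: missing baricitinib counted as non-response, and 24/240 placebo responders before imputation. The tipping placebo probability is:

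| Baricitinib responders | Placebo missing | At 0.05 | At 0.025 | First tipped value, 0.2 grid |
|---|---|---|---|---|
| 30/120 | 36 | 0.400 | 0.321 | 0.4 / 0.4 |
| 30/120 | 72 | 0.196 | 0.157 | 0.2 / 0.2 |
| 30/120 | 96 | 0.146 | 0.118 | 0.2 / 0.2 |
| 36/120 | 36 | 0.692 | 0.602 | 0.8 / 0.8 |
| 36/120 | 72 | 0.335 | 0.291 | 0.4 / 0.4 |
| 36/120 | 96 | 0.250 | 0.217 | 0.4 / 0.4 |

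On the example grid in 6.4.5 the reported value is the same in all six cases. The first case sits on the 0.4 grid point and could move.

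**6. A workable cut-off.** Set the hypothesis's own p-value to 1, hold the others as observed, run the graph, and read the level left on its node. Take two primaries that pass all alpha to each other. With p = 0.01 and 0.02, the cut-off is 0.05 for both. With p = 0.01 and 0.2, it is 0.025 for the first. In 4,000 random eight-hypothesis graphs this cut-off matched the graph's decision in 32,000 of 32,000 cases. The level at the moment of rejection depended on testing order in 271 of the 4,000, so it is a poorer choice.

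**The case against.** The strongest reply is that 0.05 is a declared convention. Tipping is a sensitivity analysis, SAP 6.2 makes 0.05 the default, and SAP 6.6 leaves other analyses unadjusted. That would settle the level of a stand-alone sensitivity test. It does not settle this one, because a tipping point is defined as losing significance, and for these hypotheses significance is gained at the graph level.

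Other parts of the reply stand:

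- **Categorical endpoints.** A reader might infer that 6.4.5 fixes 0.05 for IGA and Itch NRS as well. It does not say so. The inference rests on the word similar, the 6.2 default and the closing line of 6.6. Since 6.2 names Section 6.6 as an exception, a graph-level reading is also open. The defect there is an unstated level.
- **The two-way tables.** A reader might infer that the overstatement is hidden. Step 4 computes a p-value and is repeated for each pair of delta values to build the table, so the cells most naturally hold p-values that can be read against any level. The text does not say this outright.
- **Which endpoints are tipped.** The 6.4.5 list and Table JAHL.6.5 include EASI percent change. Table JAHL.6.1 gives it no tipping analysis and Table JAHL.6.3 no seed. Table JAHL.6.3 has rows the 6.4.5 list lacks, such as "Proportion of patients achieving EASI75 at Week 16; primary censoring rule". Table JAHL.6.5, as extracted, shows tipping beside SCORAD90 and only placebo multiple imputation for SCORAD75.
- **Outcomes with both primaries rejected.** Under the planning rates these are more than nine trials in ten, and no gap can be demonstrated there from the documents.

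**Conclusion.** The point holds in a limited form. It is explicit for one continuous endpoint at three doses and an inference for the categorical ones. If one IGA primary is not rejected, the 0.05 cut-off is at least twice the graph level of every rejected hypothesis, and the EASI tipping delta is overstated. The factors of 1.37, 1.16 and 1.10 apply at a level of 0.025 and rest on assumed z-values and a fixed standard error; the SD-unit figures rest on assumed missingness. The chance of about 5% to 8% rests on the SAP 6.1 rates. If both primaries are rejected, the gap may be zero.

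A reader might infer that the family-wise error is inflated or that a claim could be wrongly won. The documents do not support that: the tipping analysis feeds no confirmatory decision. The consequence is an optimistic robustness statement in some outcomes, which a short clarification removes.

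**What to change.** In SAP 6.4.5, for continuous and categorical endpoints alike:

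- Define the tipping point as the first delta, or first placebo response probability, at which the aggregated p-value exceeds the hypothesis's Section 6.6 graph level. That level is what is left on its node when its own p-value is set to 1 and the others are held as observed. It returns 0.05 whenever all alpha has reached the hypothesis.
- State that this checks one hypothesis at a time. Related endpoints share the same missing data and all doses share placebo, so a bad scenario could also lower the alpha reaching the node. The cut-off may therefore still flatter the claim.
- Print the p-values in the two-way tables.
- Label runs on hypotheses the graph did not reject as descriptive, and keep 0.05 for endpoints outside the graph.
- Reconcile the list of tipped endpoints across the 6.4.5 text and Tables JAHL.6.1, JAHL.6.3 and JAHL.6.5.

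The cost is a few sentences and one cut-off per hypothesis read from the graph program. Where the graph level is below 0.05, reported tipping points will look slightly less robust; where it is 0.05, nothing changes.
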